Protocol Title: Early Fortification of Human Milk for Very Low Birth Weight Infants and Effects on Growth Velocity

Principal Investigator: [name], DO

1. Objectives

Describe the purpose, specific aims, and hypothesis:

The purpose of this investigation is to determine whether early fortification of human milk feeds improve growth outcomes for very low birth weight infants (VLBW) (birth weight 1000-1500 grams). We hypothesize that introducing higher caloric feeds at the onset of enteral feeds will improve early growth metrics in VLBW infants as compared to infants who begin human milk fortification after the first week of life, which represents our present standard of care. The primary outcome for this study is growth velocity (g/kg/day) at 28 days of life.

2. Background

Describe the background and rationale for the study:

Human milk, maternal or donor milk, is the standard of care for feeding premature infants. However, human milk alone does not provide sufficient energy, protein, fat, and micronutrients to meet the demands of the VLBW premature infant. Thus, slow growth can persist for preterm infants and catch-up growth can be incomplete even after discharge from the NICU, and slow extra-uterine growth (weight, length, and head circumference) is associated with poor neurodevelopment and lower intelligence in school age children born preterm. Using human milk fortifiers (HMF) increase nutrient density of human milk and allows for infants to maintain a human milk-based diet, which has been shown to reduce the incidence of necrotizing enterocolitis (NEC) and improve cognitive outcomes in preterm infants.

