Fortification of human milk is institution-specific and no standard of care has been recommended regarding the timing of fortification of human milk feeds in preterm infants. Much of the concern for earlier fortification arise over whether comorbidities, such as NEC and feeding intolerance, will be more prominent in infants provided early fortification versus delayed fortification. To date, no studies have demonstrated a relationship between human milk fortifiers and the incidence of NEC or feeding tolerance. Thus, delays in introducing HMF may represent an unwarranted safety concern that interferes with supplying an appropriate nutrient-enriched diet to preterm infants. For example, 34.3% of preterm infants are diagnosed with post-natal growth failure at the Children's Hospital of Georgia. Further, later introduction of HMFs may lead to longer time to reach full enteral feeds, total duration on total parenteral nutrition (TPN), or duration of central venous line use. Current available evidence suggests that fortification of human milk starting at the first feed is safe and well-tolerated and may have substantial benefit for preterm infant growth.

3. Inclusion and Exclusion Criteria

List the inclusion/exclusion criteria:

Inclusion:

1. Birth weight 1000-1500 grams
2. Admitted to AU NICU within 24 hours of life
3. Maternal intent to use human milk (maternal or donor milk)

Exclusion:

1. Congenital anomalies including congenital heart disease or other major defect requiring surgical intervention
2. Feeds not started within first 96 hours of life
3. Intrauterine growth restriction (IUGR) defined as <3rd % on a gender specific Fenton growth curve

4. Number of Subjects/Records/Samples Collected

Indicate the total number of subjects to be accrued/records reviewed/samples collected across all sites:

The sample size was determined assuming an alpha level of 0.05, power of 80%, a common standard deviation of 3.64, and a two-sided two-sample t-test to examine differences in weight growth velocity at 28days between the two feeding protocol groups. The mean for the standard of care group (fortification beginning on day 8) was 10.6% and for the intervention group (fortification beginning on day 1) was 12.3, 12.6 and 13.6. The sample size required for each mean difference is below

Assumed Mean in Each Group		Sample Size 2. per Group
Fortification Day 8	Fortification Day 1	
10.56	12.25	74
10.56	12.56	53
10.56	13.56	25

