A sample size of 25 per group, for a total of 50 subjects will be needed.

5. Recruitment Methods

Describe when, where, and how potential subjects will be recruited:

All neonates admitted to the NICU who have a birth weight of 1000-1500 grams will be eligible for this study. Screening will include chart review to ensure inclusion criteria is met. Parents (legal guardians) of eligible neonates will be approached for study participation by the PI or co-Investigators.

6. Multiple Site	 N/A
7. Reliance Agreements/Single IRB	 N/A

8. Procedures Involved

a. Describe the procedures involved to include those procedures that are standard evaluation and/or care and those that are solely for research purposes:

Feeding Protocol

All VLBW infants in AU's NICU are provided a standard feeding protocol that has been in use since 2011 and includes fortification of human milk with Enfamil High Protein Liquid Human Milk Fortifier (HP HMF) on feeding day 8. Study participants will be randomly assigned to receive standard of care (ie fortification on feeding day 8) or fortification on feeding day 1. In general, feedings for preterm infants are started in the first 48 hours.

b. Describe and explain the study design:

If the study involves multiple conditions where each condition involves different procedures, please provide a table that breaks down the procedures by condition and in chronological order. Include when and where they are performed.

1. Subjects will be randomly assigned to one of two groups using blocked randomization to ensure equal allocation throughout enrollment. Blocks of size 4 and 6 will be randomly determined and then the group assignment will be randomly permuted within each block. Initiation of enteral feedings, enteral volume advancement, and weaning off parental nutrition will follow the standardized NICU feeding protocol.
2. Subjects will be fed a diet of human milk per standard NICU feeding protocol. Should maternal milk supply be inadequate to meet daily volume needs, donor milk will be used per standard NICU feeding protocol. Importantly, mothers (or guardians) must provide written consent for donor human milk. This consent is separate from the study consent and will be required for study participation.
3. Enfamil High Protein Liquid Human Milk Fortifier (HP HMF) will be used to fortify maternal milk.

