Briefly describe the actual source records or measures that will be used to collect data about participants. (All surveys, interview scripts, and data collection forms will be attached elsewhere in the application. Do not add other documents to the protocol.) Describe what data will be collected and how it will be collected at all measurement/data collection time-points.

Data will be collected from the patient's EMR. Data to be collected include: date of birth, gender, estimated gestation age (EGA), Apgar score at 1 and 5 minutes, weights, head circumference, length, z-scores for weight, length, and head circumference, total volume of feeds and TPN, number of missed enteral feeds, maternal milk vs donor milk volumes. Laboratory data including basic metabolic panel, magnesium, phosphorus, alkaline phosphatase and urine sodium, potassium and magnesium will be collected on day 22 as per the current standard of care. No blood collections or other procedures will be performed specifically for the study. Clinical outcomes will be collected to include: incidence of metabolic acidosis, NEC, oxygen requirement at 36 weeks, PDA, and death.

Anthropometrics

Anthropometrics are measured as part of the standard physical assessment of the preterm infant. For this study, all anthropometric measurements and calculations will follow AU's standard preterm infant physical assessment guidelines.

Weight

1. Body weight will be measured within 24 hours of birth and then every 7 days until 28 days of life and again at 36 weeks post-menstrual age (PMA).
2. Measurement of weight will be performed by the principal investigator (PI) and/or co-Investigators
3. Weight will be measured (x 2) on a tared infant scale calibrated to the nearest 10 grams. Weights will be recorded in grams (g). Discrepancies of greater than 20g will be repeated.
4. Infants will be weighed without a diaper.
5. Average weight will be recorded in the EMR and documented in the database.
6. Weight will be plotted on a gender-specific Fenton growth chart in the EMR and the percentile recorded in the database

Weight Gain

1. Weight gain and growth velocity (GV) will be calculated at 28 days of life and 36 weeks PMA.
2. Weight gain will be recorded as g/day
3. GV will be calculated as follows and recorded in the database:

$$GV \text{ (g/kg/day)} = \frac{[1000 \times (Wn - W1)]}{(Dn - D1) \times \left[\frac{Wn + W1}{2} \right]}$$

W= weight in grams

D = day

1 = interval of time chosen

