- e. Milk collection labels with a unique bar-code generated by the Cerner Bridge® bar-code system

2. All breastmilk will be processed and prepared in the NICU Milk Lab by trained technicians per standard policy and procedure.
3. The Cerner® Bridge label on each container of breastmilk will be scanned and recorded into the Cerner® Bridge breastmilk management system.
4. All containers of mother's milk collected in one 24 hour span of time will be pooled into a single container per standard NICU Milk Lab procedure. Expiration date and times will be adjusted by Cerner® Bridge once each container is scanned and combined.

2. *Describe the procedures performed to lessen the probability or magnitude of risks:*

As the only intervention that deviates from current standard of care is the use of HMF from feeding day 1 to feeding day 7, we do not anticipate any unique risks for study participants in either group. All SOPs for the handling of human milk and bedside feeding will be followed.

3. *Describe the duration of an individual subject's participation in the study and the time involved also include the overall duration of the project:*

Neonates will be enrolled in the study from birth until 36 weeks post-menstrual age or discharge from the NICU, whichever comes first. Estimated time in the study is two to twelve weeks depending on gestational age at birth.

9. Data and Specimen Management

a. Describe the data analysis plan, including any statistical procedures:

All statistical analysis will be performed using SAS 9.4 and statistical significance will be assessed using an alpha level of 0.05. Descriptive statistics within fortification group (day 1 or day 8) will be determined including means and standard deviations for continuous variables, frequencies and percentages for categorical variables, and medians and interquartile ranges for ordinal variables. Distributional assumptions will be examined before testing and if violations to the assumptions occur a transformation or nonparametric methods will be used. Missing data will not be imputed.

N/A

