To examine differences between the two groups and assess for potential confounding variables two-sample t-tests will be used for continuous variables, chi-square tests will be used for categorical variables, and Wilcoxon Rank Sum tests will be used for ordinal data. Variables that will be examined include all collected EMR data (e.g., demographics, feeding related, laboratory, and clinical measures) and anthropometric measures.

To examine differences between the two groups (day 1 vs. day 8), a simple two-sided two-sample t-test will be used as a preliminary test for differences in continuous outcomes (e.g., weight growth velocity, head circumference growth velocity, length growth velocity, zscores). Then, to control for various potential confounders or covariates, analysis of covariance (ANCOVA) will be used with the main effect of interest being the group effect. Covariates that will be adjusted for include gestational age, total number of feed interruptions, incidence of metabolic acidosis, and NEC. Because there are only two groups, no adjustment to the overall alpha level will be needed to control for multiple comparisons.

b. When applicable, provide a power analysis:

N/A

The sample size was determined assuming an alpha level of 0.05, power of 80%, a common standard deviation of 3.64, and a two-sided two-sample t-test to examine differences in weight growth velocity at 28days between the two feeding protocol groups. The mean for the standard of care group (fortification beginning on day 8) was 10.6% and for the intervention group (fortification beginning on day 1) was 12.3, 12.6 and 13.6. The sample size required for each mean difference is below

Assumed Mean in Each Group		Sample Size per Group
Fortification Day 8	Fortification Day 1	
10.56	12.25	74
10.56	12.56	53
10.56	13.56	25

A sample size of 25 per group, for a total of 50 subjects will be needed.

c. Describe how data and specimens will be handled:
 
Data will be collected and recorded on a coded spreadsheet that is stored on a research specific Box drive assigned by AU IRB.
	 N/A

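### Participation and withdrawal rules can remove infants before the day-28 primary outcome: the protocol makes no provision to keep their weight and states no loss allowance

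*Protocol*

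**What the plan says.** **Outcome and schedule.** Section 1: "The primary outcome for this study is growth velocity (g/kg/day) at 28 days of life". Section 8 (Weight) has body weight taken within 24 hours of birth, "then every 7 days until 28 days of life and again at 36 weeks post-menstrual age (PMA"), which treats 36 weeks PMA as a later visit. It also states: "Anthropometrics are measured as part of the standard physical assessment of the preterm infant".

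**End of participation.** Section 8 (duration): "Neonates will be enrolled in the study from birth until 36 weeks post-menstrual age or discharge from the NICU, whichever comes first". It continues: "Estimated time in the study is two to twelve weeks depending on gestational age at birth".

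**Withdrawal.** Section 11a lists five grounds: parental request, the attending neonatologist's judgement, need for formula or modular additives, NEC at Bell stage IIb or above, and gastrointestinal perforation. Section 11c, the place for procedures on withdrawal and any continued data collection, is marked not applicable and has no text. Section 9a says that missing data are not imputed.

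**Sample size.** Section 4 answers the prompt "Indicate the total number of subjects to be accrued/records reviewed/samples collected across all sites" with "A sample size of 25 per group, for a total of 50 subjects will be needed". Section 9b repeats the number. Its basis is given as "The sample size was determined assuming an alpha level of 0.05, power of 80%, a common standard deviation of 3.64", with a two-sided two-sample t-test. Neither section mentions loss.

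**The concern.** The outcome is fixed at day 28, but two sets of rules can take an infant out of the study before then.

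The first is the end of participation, which for some infants falls before day 28. The second is withdrawal for events after randomisation, three of which concern feeding or the bowel. With nothing collected afterwards and nothing imputed, these infants would drop out of the primary comparison.

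The main stake is bias. Section 12a names a minimal risk of feeding intolerance and a possible increase in NEC with early fortification. If withdrawal on those grounds is more common in one arm, the infants left in the two arms are no longer comparable as randomised. A larger sample would not cure that.

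The lesser stake is power. The accrual number equals the smallest number of infants with an outcome that gives 80%.

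**Working it through.** **1. Timing.**
- Inputs: outcome on day 28 (section 1); participation ends at 36 weeks 0 days PMA or discharge (section 8); birth weight 1000 to 1500 g, infants below the 3rd percentile excluded, no gestational-age limit (section 3).
- PMA on day 28 is gestational age at birth plus 28 days. The PMA limit therefore comes before day 28 for any infant born after 36w0d − 28 days = 32w0d.
- Where the stay ends at 36 weeks PMA, the two-to-twelve-week estimate corresponds to births at 36 − 2 = 34 weeks and 36 − 12 = 24 weeks. The lower end, 14 days, is 28 − 14 = 14 days short of the outcome.
- The weight ceiling and the percentile exclusion limit how many infants born after 32w0d are eligible. The protocol does not allow that share to be calculated.
- An infant past 36 weeks PMA but still in the NICU has routine weights in the medical record, so for that infant this is a conflict of wording. Only discharge before day 28 physically loses the weight.

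**2. Withdrawal, set side by side.**
- 11a: withdrawal is required on feeding and bowel grounds that arise after randomisation.
- 11c: nothing is described for data after withdrawal. The not-applicable box alone would prove little, since it is also ticked at 12a, where text follows; at 11c there is no text.
- 9a: no imputation.
- 12a: early fortification may affect feeding tolerance and NEC.

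Taken together, the plan as written drops infants on grounds that its own risk section says the intervention may influence.

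**3. The sample size.**
- Inputs: SD 3.64, two-sided alpha 0.05, differences 12.25 − 10.56 = 1.69, 12.56 − 10.56 = 2.00, 13.56 − 10.56 = 3.00 (section 4).
- Power is the probability that |T| exceeds the critical t value on n₁ + n₂ − 2 degrees of freedom, where T is noncentral t with λ = δ / [σ√(1/n₁ + 1/n₂)].
- The plan's own figures reproduce: 74 per group at 1.69 gives 80.1%, 53 at 2.00 gives 80.0%, 25 at 3.00 gives 81.5%. At 3.00, 24 per group gives 79.8%, so 25 is the smallest equal group size reaching 80%.
- At a difference of 3.00, by number with an outcome:

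| Evaluable | λ | Power |
|---|---|---|
| 25/25 | 3 / (3.64 × 0.2828) = 2.91 | 81.5% |
| 25/24 (one lost) | 3 / (3.64 × 0.2858) = 2.88 | 80.6% |
| 24/24 (two lost) | 3 / (3.64 × 0.2887) = 2.86 | 79.8% |
| 23/22 (10% lost, assumed) | 3 / (3.64 × 0.2982) = 2.76 | 77.1% |
| 20/20 (20% lost, assumed) | 3 / (3.64 × 0.3162) = 2.61 | 71.9% |

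- The difference detectable with 80% power is 2.94 with 50 outcomes, 3.11 with 45 and 3.31 with 40. The largest difference in the protocol's table is 3.00.

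**The case against.** **No printed figure is wrong.** This stands. All three rows of the table are correct. A reader might infer that the trial is underpowered or that 50 must be raised, but the documents do not support that. They give no loss rate, one or two losses hardly matter, and the shortfalls at 10% and 20% follow from assumed rates. Section 9b, read as a power analysis, can fairly mean the number analysed; only section 4 presents the figure as accrual.

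**ANCOVA may recover the power.** This is possible. One covariate explaining about 7% of the variance (10% loss) or 18% (20% loss) would restore 80%, and gestational age is a planned covariate. The protocol claims no such gain, and adjustment does not guarantee removal of bias from selective loss.

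**Early discharge may be rare.** This stands as a limit on the point. By the protocol's own velocity formula, a 1500 g infant growing at 10.56 to 13.56 g/kg/day over 28 days weighs about 2020 to 2203 g. No discharge criterion is given, so frequent discharge before day 28 is not shown. The two-week estimate shows only that short participation is contemplated.

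**Withdrawal may be rare and balanced.** This stands in part. Donor milk covers a short maternal supply, and separate consent to it is required for participation (section 8), which narrows the formula route. Section 12a calls the intolerance risk minimal, section 2 reports no demonstrated link of fortifiers with NEC or tolerance, and section 8 expects no unique risks. A reader might infer that arm-dependent loss is established. It is not; it is only a possibility that section 12a itself raises.

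**The analysis set belongs in the statistical analysis plan.** This is fair for the analysis set. Whether the weight is collected after withdrawal is settled in the protocol, and no analysis plan can use a weight that was never collected.

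**Conclusion.** The point holds as a gap in outcome collection, with a minor clarification of the sample size.

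Section 8's end of participation conflicts with a day-28 primary outcome, and section 11 withdraws infants after randomisation without keeping their outcome. The resulting loss could depend on the arm. Neither its size nor its direction can be derived from the protocol. The conclusion rests on reading sections 8, 9a, 11a and 11c as written and on the risks named in 12a.

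The power element is secondary. The 80% belongs to 25 infants per group with an outcome, at the largest of three assumed differences. It would become about 77% or 72% only if 10% or 20% were lost, and both rates are assumptions.

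**What to change.** 1. **Section 8:** reconcile the end of participation with the day-28 outcome, so that the day-28 weight is used for every infant still in the NICU, including those already past 36 weeks PMA.
2. **Section 11c:** replace the empty entry with a provision to take the routine day-28 weight from the medical record after withdrawal, unless the parent withdraws permission, and to include it in the primary analysis by randomised group. The withdrawal criteria themselves need no change for this purpose.
3. **Sections 4 and 9b:** state that the 80% applies to 25 evaluable infants per group at a difference of 3.00 and includes no loss allowance. Give the power at an expected loss rate, counting infants discharged before day 28, with the rate labelled as an assumption. Keep the target of 50.

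**Cost:** small changes to the protocol and possibly the consent wording, and a slightly less favourable stated power. No infants are added. A routine weight may not follow the study procedure in section 8 (two weighings, no diaper, by the investigators), so the source of each weight should be recorded. Infants discharged before day 28 remain a loss.

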4. Parenteral nutrition will be provided as outlined in the standard NICU feeding protocol and will be consistent with parenteral intake provided to all VLBW infants in the NICU regardless of study participation.
5. Enfamil HP HMF will be added to provide 22 calories/ounce on the initiation of enteral feeds for the intervention group (feeding day 1). For the control group, Enfamil HP HMF will be added to provide 22 calories/ounce when enteral feeding volume reaches 80 mL/kg/day (feeding day 8). Caloric density will be advanced to 24 calories/ounce at feeding day 10 for both groups. The caloric density progression follows the standard NICU fortification practices.

Blinding Procedures

Feeding tolerance is largely subjective. As an important secondary outcome, we will blind all healthcare personnel to study group allocation for the first 7 feeding days.

1. Upon consent, participants will be randomized to one of two study groups.
2. The milk bank in the NICU is responsible for all human milk preparation. Milk bank technicians will receive the group allocation for each participant and prepare human milk with/without fortification according to standard formulations.
3. Group allocation for each participant will be recorded by milk bank technicians on the daily feeding sheets (standard procedures for all infants). Group allocation and fortification will be confirmed by one study member of the study team who will be unblinded (co-Investigator [name] who is the NICU dietitian that oversees the milk laboratory).
4. Blinding will be accomplished by removing the caloric content from the label for all study participant. In the field that contains calories, “study participant” will be entered. Blinding will occur during the first 7 feeding days and calorie content will be recorded on feeding day 8 and all subsequent feeding days.

Intervention Group

	Parenteral Nutrition/IV Fluids				Enteral Feedings Given by 30-60 minute bolus q 3 hours NG/OG		Intervention Group
Feeding Day	Glucose mg/kg/min	Protein, g/kg	Lipids, g/kg	IVF, mL/kg	Enteral Feedings, mL/kg	Feeding Type	Notes
Day 1	6-10	3.5-4	3	80-130	20	Human Milk +HP HMF	Add Enfamil High Protein Human Milk Fortifier to 22 calories
Day 2	6-10	4	3	80-130	20	Human Milk +HP HMF	
Day 3	6-10	4	3	90-110	40	Human Milk +HP HMF	
Day 4	6-10	4	3	90-110	40	Human Milk +HP HMF	
Day 5	6-10	4	3	70-90	60	Human Milk +HP HMF	
Day 6	6-10	3-4	3	70-90	60	Human Milk +HP HMF	
Day 7	6-10	2.5-4	2	50-70	80	Human Milk +HP HMF	

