6. Data folders in use during testing will not contain personal identifiers. Any study information about subjects will only be given out with the parent's or legal guardian's permissions. If the results of this study are published, the names of the subjects will not be used.
7. Purging or destroying data will be done by shredding documents. PHI no longer needed will be deleted from databases.

15. Incomplete Disclosure, Authorized Deception, or Deception

N/A

16. Consent Process

If you are obtaining consent of subjects describe the consenting process. Be sure to include the process to be used if enrolling illiterate, non-English speakers, individuals with impaired decision making capacity to consent, as applicable.

1. Written consent will be obtained prior to performing any study related procedures with the exception of the collection of weight, length, and head circumference within the first 24 hours of life. Under some circumstances, mother (or guardian) may not be approached for study participation or be able to provide consent within the first 24 hours (e.g. maternal co-morbidity or in-patient at outlying hospital). As collection of these metrics are standard for each patient admitted to the NICU and do not represent additional risk to the potential participant, we may collect these measurements prior to consent. If consent is not obtained, measurements will be included in the EMR but will not be included in any study database.
2. The subject's mother (or guardian) will provide written consent and HIPAA authorization using the current version of the IRB-approved forms. Consent from the father will be obtained if required by the local IRB in accordance with IRB requirements.
3. The PI (or co-I) will be responsible for obtaining informed consent and HIPAA authorization after the study has been explained and all questions answered. The original signed consent form will be filed in the subject's record in accordance with institutional policy and a copy will be provided to the subject's parents/legal guardian.
4. If a protocol amendment requires revision to the informed consent form, the revised IRB approved form will be used to obtain and document re-consent from the subject's parent/legal guardian for all subjects enrolled in the study.
5. The language of the consent documents will be English.

17. Compensation for Research-Related Injury

This section is not required when research involves no more than Minimal Risk to subjects. **N/A**

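### The unblinded co-investigator is not barred from recruiting and, with blocks of 4 and 6, could guess the next arm correctly about 69% of the time (50% by chance)

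*Protocol*

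**What the plan says.** **Sequence.** Section 8.b, item 1 calls for "blocked randomization to ensure equal allocation throughout enrollment" and adds: "Blocks of size 4 and 6 will be randomly determined and then the group assignment will be randomly permuted within each block". The trial has one site (section 6 is marked not applicable) and names no stratification factor. Section 4 sets the size: "A sample size of 25 per group, for a total of 50 subjects will be needed".

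**Who recruits.** Section 5 says that parents of eligible infants "will be approached for study participation by the PI or co-Investigators". Section 16, item 3 says: "The PI (or co-I) will be responsible for obtaining informed consent and HIPAA authorization". Neither section makes an exception.

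**Who knows the arm.** Under Blinding Procedures in section 8.b, randomisation follows consent, the milk bank technicians receive the allocation, and they enter it on the daily feeding sheets. Then: "Group allocation and fortification will be confirmed by one study member of the study team who will be unblinded". That person is a co-investigator, the dietitian who oversees the milk laboratory.

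**How long the others are blind.** The reason given is that feeding tolerance is subjective, and the commitment is that "we will blind all healthcare personnel to study group allocation for the first 7 feeding days". The method is to leave the caloric content off the label. From feeding day 8 the content is shown. In the feeding schedules both arms are then at 22 calories per ounce, and both at 24 from day 10.

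**The concern.** The issue is who enrols infants, not who measures them. Read together, the sections place a person who knows the whole past sequence inside the group that may recruit the next infant. In permuted blocks the past sequence carries information about the next assignment.

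A recruiter who can anticipate the arm could, knowingly or not, influence which family is approached and when. There is some room for this: section 16 accepts that consent may come after the first 24 hours, and section 3 allows feeds to start up to 96 hours of life. With 25 infants per arm, a modest difference between arms in maturity or clinical stability would feed directly into growth velocity at 28 days and into the NEC and feeding tolerance comparisons. The planned ANCOVA adjusts for gestational age, but cannot adjust for stability that is not measured.

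**Working it through.** **Inputs from the protocol.** Two arms, 1:1; blocks of 4 and 6 in random order; 50 infants. The protocol gives neither the probability of each block size nor an enrolment rate. I take the two sizes as equally likely, and show the enrolment question as a range.

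**The plan's own figure.** The protocol states no predictability figure. The sequence length of 50 comes from a calculation "assuming an alpha level of 0.05, power of 80%, a common standard deviation of 3.64, and a two-sided two-sample t-test". Solving the t-test for differences of 1.69, 2.00 and 3.00 gives 73.8, 53.0 and 24.1 per group, which round up to the stated 74, 53 and 25. The 50 is sound.

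**Hit rate when all earlier arms are known.** The rule is to guess the arm that is behind and toss a coin when the arms are level. In a block of 2m, the expected number of correct guesses is

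m + (4^m / C(2m, m) − 1) / 2

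- Block of 4 (m = 2): 2 + (16/6 − 1)/2 = 2.833; 2.833/4 = 70.8%.
- Block of 6 (m = 3): 3 + (64/20 − 1)/2 = 4.1; 4.1/6 = 68.3%.
- Equal mix: (2.833 + 4.1)/10 = 69.3%. Any other mix lies between 68.3% and 70.8%.
- Simulation of 40,000 sequences of 50 infants: 69.0%, or 34.5 correct guesses against 25 by chance.

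Block size is not needed for this rule. The arms are level at the end of every block, so the running imbalance over the whole trial equals the imbalance within the current block. A simulated guesser who makes optimal use of the printed sizes, without knowing their order, also reaches 69.0%.

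**What the 69% consists of.** The arms are unequal before about 61% of assignments, and guesses there are right 81% of the time. The other 39% are coin tosses: 0.61 × 0.81 + 0.39 × 0.50 = 0.69. Only about 5.6% of assignments are certain; it would be 28% if the block order were known.

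**Hit rate when the most recent arms are unknown.** This is the position of any other recruiter who learns earlier arms only after the 7 feeding days.

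| Most recent infants still blinded | Correct guesses |
|---|---|
| 0 | 69.0% |
| 1 | 59.1% |
| 2 | 55.5% |
| 3 | 51.9% |
| 4 | 50.9% |
| 5 | 50.0% |

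One blinded infant removes (69.0 − 59.1)/(69.0 − 50.0) = 52% of the advantage over chance.

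**Illustration of the bias.** This rests on an assumption of mine. Suppose that selection moves expected growth velocity up by v when day-1 fortification is guessed, and down by v otherwise. The bias in the arm difference is 2v(2 × 0.69 − 1) = 0.76v. For v of 0.5 to 1.0 g/kg/day this is 0.38 to 0.76 g/kg/day, or 13% to 25% of the planned difference of 3.0. The standard error is 3.64 × √(2/25) = 1.03, so a nominal 5% error would become roughly 7% to 11%. This is a worst case: it needs a recruiter who acts on every guess.

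**The case against.** Four arguments stand against the point.

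- **Disclosure at feeding day 8.** A reader might infer that allocation becomes open to everyone once blinding ends, so that all recruiters reach 69%. The protocol does not say so. It says only that calorie content is then shown, and on the schedules that content is the same in both arms from day 8. The feeding sheets carry the allocation, but the protocol does not say that recruiters read them. This objection stands: for other recruiters, knowledge of earlier arms is possible, not planned, and even with it the rate may be close to chance.
- **Role of the dietitian.** The protocol gives this co-investigator the confirmation of allocations and the milk laboratory, and never says that this person will obtain consent. That is true, but sections 5 and 16 permit it, and a role is easily restricted in writing.
- **Limited room to select.** Eligibility is mostly objective, parents of eligible infants are to be approached without a selection step, feeds generally start within 48 hours, and randomisation follows consent. This narrows the opportunity. It does not close it, because the timing of the approach remains with the recruiter.
- **Random block sizes and ANCOVA.** Mixing sizes does reduce certainty, from 28% of assignments to 5.6%, but leaves the hit rate at 69%. Adjustment for gestational age removes part of any imbalance, but not selection on unmeasured stability.

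**Conclusion.** The point holds for one person. The protocol lets the unblinded co-investigator recruit into a single-site, unstratified sequence in small blocks, and that person could guess the next arm correctly about 69% of the time, against 50% by chance. The figure assumes knowledge of every earlier arm and depends little on the mix of block sizes (68.3% to 70.8%).

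For other recruiters the protocol neither provides for nor bars disclosure after feeding day 7. If they do learn earlier arms, their rate lies anywhere from 50% to 69%, and without an enrolment rate it cannot be narrowed.

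A reader might also take 69% as the share of assignments known in advance. It is not: half would be right by coin toss, and few are certain. Nor does the protocol show that selection will occur. This is an avoidable opening for selection bias, worth closing because closing it costs almost nothing.

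**What to change.** In sections 5, 8.b and 16, state that:

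1. the unblinded co-investigator takes no part in screening, eligibility decisions, approaching families or obtaining consent;
2. no infant's allocation, including the entry on the feeding sheets, is disclosed to anyone who screens or obtains consent until the last infant has been randomised.

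The calorie label can still be restored from feeding day 8, since on the schedules it reads the same in both arms. Nothing needs to be added on the order of consent and randomisation, which section 8.b already sets, or on the milk bank technicians, who are given no recruiting role.

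The cost is protocol wording. One co-investigator fewer can recruit, and allocations stay within the milk laboratory for longer. Feeds, sample size and analysis are unchanged.
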